13.1.4. AE and / or SAE registration

The investigator is responsible for recording all AEs / SAEs observed during the trial, that is, from the moment the subject gives informed consent until the end of the trial visit or until the last follow-up visit.

When an AE / SAE occurs, it is the investigator's responsibility to review all documentation (eg, hospital progress notes, laboratory reports, and diagnostic reports) related to the event.

The researcher must then record the information of all relevant AE / SAE in the eCRF.

SAE must be reported to the sponsor within 24 hours.

It is not acceptable for the investigator to send photocopies of the subject's medical records to the sponsor instead of completing the AE / SAE screen in the eCRF.

There may be instances in which copies of medical records for certain cases are requested by the sponsor. In this case, all the identification data of the subject, with the exception of the subject number, will be deleted in the copies of the medical records before they are sent.

The investigator should try to establish a diagnosis of the event based on the signs, symptoms, and / or other clinical information. Whenever possible, the diagnosis (not individual signs / symptoms) will be documented as AE / SAE.

The investigator should document and medically evaluate Adverse Events of Special Interest (AESIs) and overdose cases, and the result should be described on the SAE / AESI / overdose / misuse report form.

The investigator should document and medically evaluate the pregnancies, and the outcome should be described in the pregnancy notification form to be sent to the sponsor.

13.1.5. Monitoring of AE and SAE

The investigator is obliged to perform or coordinate the performance of supplementary measurements and / or evaluations as medically indicated, or as requested by the sponsor to elucidate the nature and / or causality of the AE or SAE as completely as possible. This may include laboratory tests or investigations, histopathological examinations, or additional consultation with other health care professionals.

If a subject dies during trial participation or during the follow-up period, the investigator will provide the sponsor with a copy of all post-mortem findings, including histopathology.

New or updated information will be recorded in the eCRF that was originally completed.

The investigator will send the updated data on the SAE to the sponsor within 24 hours of becoming aware of the information.

13.1.6. AE report

It is the investigator's responsibility to document all AE that occur during the trial in the source documents. AEs should be obtained by non-leading questions to the participant, for example, "Have you had any new or changed symptoms since we last asked / since your last visit?".

The researcher must document all AE that occur during the observation period established in this protocol on the eCRF screens provided.

The following approach to documentation will be taken:

All adverse events (whether serious or non-serious) to be reported should be documented on the "Adverse Event" screen of the eCRF. All AE will be described using the sign, symptom, or medical diagnosis of AE in the eCRF with standard medical terminology, in order to avoid the use of imprecise, ambiguous or colloquial

expressions. Each AE will be defined as serious or not serious according to the definitions in the previous section. The investigator will evaluate the severity of each AE and the causal relationship of the event with the study vaccine.

13.1.7. SAE report

If the AE is **serious**, the investigator will need to complete and sign, in addition to the "Adverse Event" screen of the eCRF, an "SAE / AESI / Overdose / Misuse Report Form" at the time the SAE is detected.

Transmission of the SAE / AESI / Overdose / Misuse report form by email or fax is the preferred method of transmitting this information to the sponsor / medical monitor or coordinator.

This form should be marked as an "initial" report and sent immediately (ie within 24 hours of becoming aware of the SAE) to the sponsor.

The investigator will document the date that any employee / co-investigator first became aware of the report. All SAE reports (initial and follow-up reports) will be sent to the regulatory authority National Institute of Health (Instituto Nacional de Salud – INS) within 7 days after the SAE.

Initial notification by phone does not replace the need for the investigator to complete and sign the EAS report form within designated reporting periods.

The **"initial SAE report"** should be as complete as possible, including an assessment of causation, details of the current illness and AEs, the reason the event was considered serious, the date of start and end date (if applicable), diagnostic procedures and treatment of the event, relevant medical history and concomitant medications and vaccines, as well as actions taken with the study vaccine (s). The SAE report form **must be signed by the investigator or his / her authorized designee (s).**

Investigator should inform the sponsor of the Adverse Events of Special Interest (AESI) and overdose cases by applying the same SAE reporting rules and timelines.

- a. Determination of predictability, baseline safety information: The sponsor will determine the predictability in accordance with the baseline safety information provided in the current Product Data Sheet. Any substantial update or amendment will be considered accordingly.
- b. Observation periods: For the purposes of this trial, the observation period for the collection of AE that are required to be reported in the CRFe extends from the time the subject gives informed consent to the end of the trial.

All AEs that occur in the course of the clinical trial, regardless of causal relationship, should be controlled and followed up until the result is known or it is clear that no further information can be obtained.

There must be documented reasonable attempts to obtain the monitoring information and results.

It is the investigator's responsibility to ensure that any necessary additional therapeutic measures and follow-up procedures are performed.

c. Post-trial events: If the investigator becomes aware of any SAE that occurred after the end of the trial, but is considered to be a consequence of the study vaccine (s), this should be reported to the sponsor.

Sponsor will process these SAE.

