3. STUDY TIMELINE

STUDY TIMELINE_SCHEDULE OF EVALUATIONS							
Visit Number	1	2	3	4	5	6	
Day of Study	Screening	D0	D3	D7	D28	D180-200	
Activities							
Informed Consent	x						
Medical History Review		x					
Vital Signs		х	х	х			
Complete Physical Examination		x	x	x			
Targeted Physical Examination		x	x	x			
Pregnancy Prevention Counseling	Х*						
Pregnancy Test	x						
Eligibility Confirmation	Х						
Enrollment CRF		х					
Randomization		х					
Compensation		х	х	х	х	х	
Vaccination /Product Administration (filling form)		x					
Injection Site Evaluation		х	х	х			
Adverse Event Evaluation		х	х	х			
Phone Contact (clinic visit if needed)/filling forms			x	x	x	x	
Respiratory surveillance twice a week during influenza season (acute illness detection, sample collection, storage, filling forms)							
Blood sample		х			х	x	
РВМС		х		х	х		
Storage of samples		х		x	х	x	
Packaging/Shipping						х	

*in case a reevaluation is required, it will be scheduled in 1 to 4 weeks

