10.12 Schedule of study activities

Day of Study	Event/Activity	Forms to be completed (Annex)
Day 0	Screening/Enrollment/Vaccination	Screening Form Enrollment Survey Vaccination Form
Day 3	Day 3 Post-Vaccination Follow-up	Day 3 Post Vaccination Follow-up Form
Day 7	Day 7 Post-Vaccination Follow-up	Day 7 Post Vaccination Follow-up Form
Day 28	Day 28 Post-Vaccination Follow-up/blood sample collection	Day 28 Blood collection Form
End of Season	End of Season Survey/blood sample collection	End of Season Survey

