13. ASSESSMENT OF SAFETY

Study staff will contact participants on day $3(\pm 2)$ and day $7(\pm 2)$ to ask about potential adverse effects or reactions participants might have developed after vaccination. This evaluation may be both face-to-face and virtual, especially considering that, due to the effects of the pandemic, face-to-face assistance could be affected. In addition, participants may report adverse events at any time to study personnel. Contact information will be provided at enrollment. Any adverse event will be investigated (Appendix O - INS Adverse Event Report Format) and participants will be referred to an independent physician for evaluation. The management and reporting of adverse events will be carried out taking into account the definitions and procedures detailed below.

13.1. Adverse events: definitions and procedures for recording, evaluating,

monitoring and reporting

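### Adverse events are to be collected to the end of the trial, but no general AE/SAE enquiry is scheduled after Day 7, so later serious events, chiefly non-respiratory ones, may be missed or learned of late

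*Combined protocol and SAP*

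**What the plan says.** **The collection rule.** Section 13.1.7 defines a reporting period that "extends from the time the subject gives informed consent to the end of the trial". Section 13.1.4 makes the investigator responsible for recording all AEs and SAEs "from the moment the subject gives informed consent until the end of the trial visit or until the last follow-up visit". Section 13.1.6 adds that "AEs should be obtained by non-leading questions to the participant", with an example asking what has changed since the previous contact. It names no visit days.

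**The schedule.** In Section 3 the row "Adverse Event Evaluation" carries three marks, which fit D0, D3 and D7. The row "Phone Contact (clinic visit if needed)/filling forms" carries four, which fit D3, D7, D28 and D180-200. Section 10.7 places questions about reactions on Days 3 and 7, then a blood sample on Day 28, then blood and a questionnaire at season end. For Day 28, Section 10.12 lists only the "Day 28 Blood collection Form". Section 13 has staff contact participants on Day 3 (±2) and Day 7 (±2) "to ask about potential adverse effects or reactions participants might have developed after vaccination". Beyond that, "participants may report adverse events at any time to study personnel".

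**Other later contacts.** The study summary (Section 2) mentions a survey on Day 28 and another at season end. Section 10.7.1 says the end-of-season survey asks about illnesses not yet reported, above all those that led to medical care. Section 10.8 provides twice-weekly contacts about acute illness for roughly 10 to 20 weeks. The variable table for objective 6 in Section 11.1 gives as its source for serious events the visits, calls and surveys of follow-up, plus hospital admissions.

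**The concern.** The rule and the schedule do not match. Staff who follow Sections 3, 10.7, 10.12 and 13 as written would make no general enquiry about adverse events after the Day 7 contact, although Sections 13.1.4 and 13.1.7 hold them responsible for events up to the final visit.

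Three parts of the plan depend on later events being found:

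- Objective 6 compares the proportions with anticipated and with serious events between arms by a Z test (Section 11.1).
- The halting rule in Section 10.11 is triggered by a single related SAE, which requires that the site know of it.
- Section 13.1.7 requires SAE reports to the national authority within 7 days of the event. An event first learned of at the end-of-season contact can be months past that limit.

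Section 12 also states that the investigational vaccine is not authorised in Peru, which adds to the value of complete follow-up for serious events.

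**Working it through.** The plan gives no SAE rate, expected SAE count or power for the SAE comparison, so there is no figure of its own to reproduce. The check sets the schedule against the rule and then sizes the gap.

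**1. Does any later contact carry a general AE/SAE question?**

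| Contact | What the text assigns to it | General AE/SAE question stated? |
|---|---|---|
| D0, D3, D7 | AE evaluation (Sections 3, 10.6.4, 10.7, 13) | Yes |
| In season, twice weekly | Acute illness: cough, runny nose, feverishness or body aches (Section 10.8) | No |
| D28 | Blood sample and its form (Sections 10.7, 10.12); a survey of unstated content (Section 2) | No |
| D180-200 | Blood sample and end-of-season survey (Sections 10.7, 10.7.1) | Not in general form; asks about unreported illness, especially if medically attended |

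The objective 6 table shows an intention to find SAEs through visits, calls, surveys and hospital admissions. No procedure says who asks, when, or how admissions are identified. The objective 6 analysis text relies on data from active surveillance, which Sections 10.8 and 10.8.4 describe as surveillance for acute illness.

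**2. Length of the scheduled-enquiry window.** Inputs: last scheduled AE contact on Day 7, or Day 9 at the upper limit (Section 13); final visit on Day 180-200 (Section 3).

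- Day 7: 7/200 = 3.5% to 7/180 = 3.9%.
- Day 9: 9/200 = 4.5% to 9/180 = 5.0%.
- Days after the last scheduled enquiry: from 180 − 9 = 171 to 200 − 7 = 193.

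**3. Where SAEs would fall (illustration).** Assume a constant hazard and a 1% SAE risk per arm over the whole period; neither is in the documents. With 400 per arm (Section 10.4), 400 × 0.01 = 4 SAEs are expected per arm. By Day 7 the expected number is 4 × 7/200 = 0.14 to 4 × 7/180 = 0.16. Under this assumption nearly all SAEs occur after the last scheduled AE contact.

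**4. What under-capture costs the comparison (illustration).** Let p be the SD-arm risk, RR the true risk ratio and c the fraction captured, equal in both arms. With p₁ = RR·p·c, p₂ = p·c, p̄ = (p₁ + p₂)/2 and n = 400,

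power ≈ Φ{[p₁ − p₂ − 1.96·√(2p̄(1 − p̄)/n)] / √([p₁(1 − p₁) + p₂(1 − p₂)]/n)}.

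For p = 1%, RR = 2 and c = 1: (0.01 − 1.96 × 0.00860)/0.00859 = −0.80, so power is 21%.

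| p = 1% | c = 100% | c = 50% | c = 25% |
|---|---|---|---|
| RR 2 | 21% | 13% | 8% |
| RR 3 | 52% | 30% | 17% |

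With full capture and RR 2, power runs from 13% (p = 0.5%) to 54% (p = 3%). At such low counts the normal approximation is rough, so these figures only show the order of magnitude.

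**The case against.** A reader might infer that every SAE after Day 9 depends on the participant volunteering it, that the SAE comparison is bound to be incomplete, or that about 95% of serious events will go unseen. The documents do not support any of these.

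- **Later contacts exist.** The end-of-season survey is started by staff and asks about medically attended illness, so it should reach many serious events. The twice-weekly contacts cover any acute illness that meets the symptom definition, whatever its presumed cause, and the illness surveys ask about medical care. Section 13.1.6 is a general rule on how to ask and is not limited to Day 7.
- **The 5% figure is not a capture rate.** Enquiry looks back over time, so one question at the last visit can cover the whole interval since the previous contact.
- **No capture fraction is given.** The documents show that events may be missed, not that they will be.
- **Bias between arms is not shown.** The trial is double-blind (Section 10.9) with the same contacts in both arms, so under-capture should be largely non-differential.
- **The SAE test is weak in any case**, as the full-capture column above shows.
- **The evidence has limits.** The schedule table was read by a program, and its respiratory surveillance row shows no marks although that activity is certain. The appendix forms were not in the text reviewed and may already carry the question.

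These points narrow the harm but do not remove the mismatch. The reading of the table does not stand alone: Sections 10.7, 10.12 and 13 agree with it. No section places a general AE/SAE question at Day 28 or season end. A recall question at season end may recover an event, but too late for a report due within 7 days of it.

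**Conclusion.** The inconsistency is real and should be corrected. AE/SAE collection runs to the end of the trial, but general enquiry is scheduled only to Day 7 (Day 9 at the latest), which leaves 171 to 193 days without one. Over that time SAE detection relies largely on spontaneous reports, apart from illnesses found by in-season surveillance or the end-of-season survey. SAEs, chiefly non-respiratory ones, may be missed or learned of late.

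The consequence is lost or delayed safety information and a loss of precision in a comparison that is already weak. It is not a demonstrated bias, and the primary immunogenicity endpoint is not affected. The conclusion assumes that the schedule marks are read correctly and that the Day 28 and end-of-season forms do not already carry a general AE/SAE question. If they do, what remains is a correction to the schedules. The power and event-count figures rest on assumed SAE rates and capture fractions.

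**What to change.** 1. Reconcile Sections 3, 10.7, 10.12 and 13 with Sections 13.1.4, 13.1.6 and 13.1.7 and with the objective 6 variable table in Section 11.1. Mark an AE/SAE enquiry at the existing Day 28 and end-of-season contacts.
2. Put the non-leading question of Section 13.1.6 on the forms for those two contacts. If the forms already carry it, mark it in the two schedules.
3. In objective 6, state the windows: reactions recorded on the Day 3 and Day 7 forms analysed to Day 7, and SAEs analysed separately to the end of the trial. Section 11.1 already treats anticipated and serious events as separate dimensions, so only the time windows are missing.

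The cost is two entries in the schedules, one question at two existing contacts, slightly longer contacts and a few more events to record. No new visit is needed. Scheduled enquiry would then run to the final visit.

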13.1.8. Reports of other events

A. *Pregnancy reporting and monitoring*: Pregnancy is an exclusion criterion for enrollment in this trial, but participants could become pregnant during their active participation in this trial.

Any pregnancy in a participant who has received a study vaccine must be reported to the sponsor within 24 hours of the time the center becomes aware of its incidence through a pregnancy report form. If the participant becomes pregnant during the trial, she will not receive any additional doses of any study vaccine provided by the sponsor. The pregnancy should be followed to determine the outcome, including spontaneous or voluntary termination, details of the birth, and the presence or absence of congenital malformations, congenital anomalies, or maternal and / or newborn complications. This follow-up should be done even if the expected duration of the safety follow-up for the trial has ended.

The trial site should keep in contact with pregnant participants to obtain information on the outcome of the pregnancy.

Any complication during pregnancy (eg, gestational diabetes or eclampsia) should be considered an AE; however, these complications could result in the event being considered an SAE. Miscarriages, stillbirth, stillbirth, and reported birth defects in the baby are always considered SAE. The pregnancy itself will not be processed as SAE. The researcher will follow up the participant until the end of the pregnancy and should evaluate the outcome in the shortest time possible, but no more than 30 days after the end of the pregnancy. The investigator should notify the sponsor of the pregnancy outcome by submitting a pregnancy follow-up report.

B. *SUSAR and other regulatory reporting and monitoring*: Any Suspected Unexpected Serious Adverse Reaction (SUSAR) will be promptly reported.

The sponsor will ensure that all relevant information about a SUSAR that is fatal or life-threatening is notified to the competent authorities and the relevant IRB or IEC (s) within 7 days after the sponsor is aware of it. of such event and that the relevant follow-up information is communicated within an additional 8 days.

The sponsor will report all serious and unexpected AE, which the investigator or sponsor considers to have a presumed reasonable causal relationship (suspected serious and unexpected adverse reaction [SUSAR]), to the competent authority, to the Independent Ethics Committee involved and to the researchers, in accordance with current law.

The investigator should inform the sponsor of post-trial SUSARs that occur after the subject has completed the clinical trial.

C. *Reporting and monitoring of misuse and overdose*: Drug misuse and drug overdose should always be reported in the same format (i.e., on the SAE form) and within the same timeframes as an SAE, even if possible that do not lead to an adverse outcome.

When an "overdose" or "drug misuse" of the study vaccine occurs without an AE, the investigator will also need to complete a "SAE / AESI / overdose / misuse report form" and send it to the safety contact. of the sponsor. It should be clearly stated that no AE was observed. If there is no associated SAE, the misuse / overdose will be assessed as non-serious.

In this case, it is not necessary to complete the "Adverse Event" screen of the eCRF.

14. QUALITY ASSURANCE AND QUALITY CONTROL

14.1 Vaccine products

Records will be kept of the batch/lot, quantity and dates that investigational and control vaccine products are received and used. All unused vaccines and all empty or partially used containers will be destroyed. This disposition of the investigational and control vaccine products will be accounted for by using form "Accounting for IVP" (Appendix P).

Vaccine products will be purchased and transported with data loggers for monitoring the temperature throughout transportation and storage. CDC will test vaccine products at the beginning and at the end of the trial for vaccine potency validation.

14.2 Study procedures

All questionnaires will be piloted and refined before the study start date. CDC will follow-up every week with in-country partners to ensure that activities are taking place according to the protocol. CDC and NAMRU6 will evaluate the data collected every month for missing data, data errors and inconsistencies.

14.3 Amendments and deviations

Any amendment to the protocol should be discussed with the Sponsor Representative (e-mail, phone or SMS), recorded on Appendix Q (for internal records), then signed and dated by the Study Investigator and the Sponsor Representative BEFORE implementation. Protocol deviations should be recorded on Appendix R (for internal records), then signed and dated by at least two signatories to the protocol and reported to IRB.

15. ETHICS/PROTECTION OF HUMAN SUBJECTS

The study will undergo a local review by the Institutional Review Board (IRB) of NAMRU6 and will be registered at *ClinicalTrials.gov*. CDC will rely on NAMRU6 IRB review, under reliance agreement between CDC and NAMRU6. All participants will complete informed consent, in which they state that they understand the risks and benefits of participating in the study. Participants may withdraw from the study at any time. Informed consents will be stored at NAMRU-6. Study sites must use access control mechanisms to ensure that only uniquely identifiable, authenticated, and authorized users have access to data to which they have been granted explicit access rights. Credentials (e.g., login names and passwords) must never be shared. Any personal identifiable information (PII) must remain on local servers and is not to be downloaded onto any other device such as a personal digital assistant (PDA), laptop, or portable storage device, nor will it be included in the datasets provided to CDC (except for dates of birth). Study sites may, however, use the REDCap or other mobile application for electronic data collection so long as the following provisions are met:

- 1. Devices running the application are fully encrypted;
- 2. Devices running the application require a PIN to be entered to unlock the screen.

All study data, laboratory specimens, and reports, as well as study data collection, process, and administrative forms, will be identified by a coded subject ID in order to maintain participant confidentiality. All study data will be stored separately from study records that contain names or other PII (such as locator forms and informed consent forms).

